4. Optional Procedure: With the patient's consent, if the patient cannot receive the co-stimulated T cells, the cells will remain cryopreserved in the Stem Cell Laboratory indefinitely. The patient can receive the cells at a later date. If the patient's physician feels that the patient will no longer benefit from the cells,

the cells may be used for research or discarded. If the patient refuses, the cells will be destroyed.

Study Enrollment:

The study population for this research will consist of participants from:

Only at MDACC

Estimated Accrual:

Total Accrual at MDACC:	40
Estimated monthly accrual at MDACC:	1

Accrual Comments:

The sample size of 40 patients was chosen for logistical reasons.

Is this an NCI-Cancer Therapy Evaluation Protocol (CTEP)? No

Is this an NCI-Division of Cancer Prevention Protocol (DCP)? No

Statistical Considerations:

Overview

This is a phase II trial of infusion of autologous T cells for immune restoration in patients with CLL. The primary scientific goal is to determine the feasibility and safety of this procedure. A total of 40 patients will receive T cell infusions. Endpoint evaluation will be at day +90 after the co-stimulated T cell infusion.

Sample Size

In this trial, the sample size of 40 patients was chosen for logistical reasons. With 40 patients, a 95% confidence interval around the success rate will be no wider than 32%.

Primary Endpoint

Success will be defined as achievement of a target activated T-cell dose of $1 \times 10^8 \pm 20\%$ and the lack of dose limiting toxicity (DLT).

For this trial DLT is defined as:

- Any grade 4 or higher non-hematologic toxicity or grade 3 or 4 allergy/immunology toxicity;
- Allergic reaction or urticaria grade 3 or higher (CTC v4.03 CTCAE) by +90 days after T cell infusion;
- Grade 2 or greater autoimmune phenomena; or,
- Grade 4 or higher hematologic toxicity (with the exception of any preexisting AE due to prior treatment or due to disease) deemed related to T cells and occurring by day +90 after T cell infusion.

Feasibility is defined as achievement of the target T cell dose ($1 \times 10^8 \pm 20\%$) without DLT in > 50% of patients enrolled.

Safety Monitoring

Any death due to the infusion of co-stimulated T-Cell product itself and not disease progression will be considered unacceptable and the study will be stopped. If the study is not terminated early, it will continue

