until all patients have been treated with co-stimulated T Cells and completed all follow up evaluations.

In addition, we will use a Bayesian sequential monitoring rule to monitor the primary endpoint of the study. If there is a high probability that the overall success rate is less than 50%, enrollment into the trial will be stopped. We will enroll a minimum of 6 patients onto the study before stopping. We will use the following criteria: we will stop enrollment if at any time during the course of the trial:

$\Pr [\text{90-day success rate} > 0.50 \mid \text{data}] < 0.025$

That is, if we determine that there is a less than 2.5% chance that the 90-day success rate is greater than 50%, accrual will be stopped. We assume a beta (1, 1) prior distribution for the success rate, which has a mean of 0.50 corresponding to the target success rate. Stopping boundaries corresponding to this probability criterion are to terminate accrual if:

If there are this many patients accrued	Stop the trial if this number of patients meet criteria for success
6-7	0
8-10	0-1
11-13	0-2
14-15	0-3
16-18	0-4
19-21	0-5
22-23	0-6
24-26	0-7
27-28	0-8
29-31	0-9
32-33	0-10
34-35	0-11
36-38	0-12
39	0-13
40	Always Stop

This stopping rule was chosen to assure that the probability that the trial will stop early would be approximately 10% if the true success rate was 50%. The operating characteristics of this rule are shown in the table below.

We will enroll 3 patients and then wait till all 3 have reached +90 days without DLT before enrolling more patients. At that time point 3 additional patients will be enrolled and we will wait till they have all reached

+90 days and without DLT before enrolling the remaining patients.

Operating Characteristics for Success Monitoring Rule

If the true 90-day success rate is...	Early Stopping Probability	Achieved Sample Size		
		25th percentile	50th percentile	75th percentile
0.3	0.833	8	16	32
0.4	0.413	19	40	40
0.5	0.108	40	40	40
0.6	0.018	40	40	40
0.7	0.002	40	40	40

The monitoring rules will be assessed by the study team with assistance as necessary from the Department of Biostatistics at MD Anderson Cancer Center.

Secondary Analyses

Immune reconstitution: We will assess the percentages and absolute values of CD3+, CD4+, CD8+ and CD4/CD8 ratio and report these at each time point along with 95% confidence intervals. In addition, immune reconstitution will be compared at each time point.

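### The stopping table is indexed on patients accrued, but its boundaries fit the 90-day criterion only when indexed on patients with a known day +90 outcome

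*Combined protocol and SAP*

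**What the plan says.** Under Statistical Considerations, Safety Monitoring, the plan sets a Bayesian rule on the primary endpoint with a beta(1, 1) prior. If there is "a less than 2.5% chance that the 90-day success rate is greater than 50%, accrual will be stopped". Looks are not tied to fixed times: "we will stop enrollment if at any time during the course of the trial" the criterion is met.

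The table is presented as following from this criterion: "Stopping boundaries corresponding to this probability criterion are to terminate accrual if". Its first column is headed "If there are this many patients accrued", and its second gives the number meeting the success criteria at which the trial stops. The rule is said to assure that "the probability that the trial will stop early would be approximately 10% if the true success rate was 50" (per cent). The table of operating characteristics prints 0.108 for that case and gives quartiles of "Achieved Sample Size".

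On timing, the Overview says: "Endpoint evaluation will be at day +90 after the co-stimulated T cell infusion". The study plan allows 14 days for cell expansion before infusion, and Estimated Accrual gives 1 patient per month. Enrolment waits for day +90 after the first 3 patients and again after the next 3. No wait is stated for patients 7 to 40.

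**The concern.** A posterior for a 90-day success rate can use only patients whose outcome is known, whereas a count of patients accrued includes those still waiting. The two counts agree while the hold covers the first 6 patients and part company afterwards. No rule says whether a pending patient is left out, counted as not yet a success, or counted as a success so far.

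The table is the tool the study team will use. The plan gives the assessment to that team, with help from Biostatistics as necessary, and lists no data safety monitoring board. Two teams with the same data could therefore reach opposite decisions, one from the formula and one from the table. The stated early-stopping probabilities would then describe neither team's practice for certain.

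**Working it through.** **Inputs.** From Safety Monitoring: beta(1, 1) prior, target 0.50, cut-off 0.025, minimum of 6 patients. From the Overview: maximum of 40, endpoint at day +90. From Estimated Accrual: 1 per month. From the study plan: 14 days of expansion.

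**1. Reproducing the plan.** With s successes in n patients of known outcome, the posterior is Beta(1+s, 1+n−s), and the boundary b(n) is the largest s with P(Beta(1+s, 1+n−s) > 0.5) < 0.025. All 34 boundaries for n = 6 to 39 match the table. An exact binomial recursion, checking after every patient from 6 to 39 with outcomes known at once, gives early stopping of 0.8332 / 0.4131 / 0.1077 / 0.0178 / 0.0021 at true rates 0.3 to 0.7. The plan prints 0.833 / 0.413 / 0.108 / 0.018 / 0.002. The quartiles at 0.3 (8, 16, 32) also match. The plan's own figures therefore rest on n being patients with known outcomes.

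**2. How many are pending.** The wait is 90 days from infusion, or 90 + 14 = 104 days if counted from the start of expansion. At 1 patient per month, a look just before or just after an enrolment finds 2 or 3 pending (90 days), or 3 or 4 pending (104 days).

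**3. Where table and criterion disagree.** For this prior, P(p > 0.5 | s of n) = P(Bin(n+1, 0.5) ≤ s).

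- 8 accrued, 6 evaluated, 1 success. Row 8–10 (0–1) says stop. The posterior on 6 evaluated is (1 + 7)/128 = 0.0625, so the criterion says continue, as does row 6–7. The row is right for 8 evaluated patients: (1 + 9)/512 = 0.0195.
- 11 accrued, 8 evaluated, 1 success, with the 3 pending patients counted as successes so far. The count is 4, and row 11–13 (0–2) says continue. The posterior on the 8 evaluated is 0.0195, so the criterion says stop.

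**4. Effect on early stopping.** Treat the 3+3 hold as a pause, so the first 6 are evaluated. Then, with L pending, the number evaluated at n accrued is e = max(6, n − L), and S is the number of successes among them. Three readings follow:

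- non-success: stop if S ≤ b(n)
- provisional success, no failure known early: stop if S + (n − e) ≤ b(n)
- evaluated only: stop if S ≤ b(e)

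| Reading (L = 2 / 3 / 4) | True rate 0.5 (printed 0.108) | True rate 0.3 (printed 0.833) |
|---|---|---|
| Pending = non-success | 0.224 / 0.280 / 0.363 | 0.902 / 0.925 / 0.947 |
| Pending = provisional success | 0.038 / 0.027 / 0.021 | 0.66 / 0.56 / 0.45 |
| Evaluated only | 0.105 / 0.105 / 0.101 | 0.815 / 0.815 / 0.787 |

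At a true rate of 0.6 the non-success reading gives 0.063 / 0.086 / 0.133 against 0.018 printed. With only 1 pending patient, the first two readings already give 0.154 and 0.061 at 0.5.

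The evaluated-only figure at 0.3 falls slightly below 0.833 because the last boundaries are reached too late to stop accrual. With L = 3, only 36 patients are evaluated when 39 have been accrued.

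**5. Sample size.** Under the evaluated-only reading at a true rate of 0.3, the quartiles stay at 8 / 16 / 32 evaluated patients. As enrolled patients they become 10–12 / 18–20 / 34–36 if failures count only at day +90. The printed quartiles do not say which count is meant.

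**The case against.** The strongest reply is that the criterion governs. The operative sentence is about the posterior probability, the table is presented as derived from it, and Biostatistics is available. A statistician would index the rows on evaluated patients, and the roughly 10% target then holds (0.101 to 0.105). This stands as the sensible reading and is why the repair is small. It does not settle the matter: the column heading says otherwise, looks are allowed at any time, and the plan has no rule for pending patients.

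A reader might infer that the trial as written would stop about 2 to 3.4 times as often as stated (0.224/0.108 to 0.363/0.108). The documents do not support that as an unconditional claim, because it needs pending patients to count as non-successes. The primary endpoint reads "Success will be defined as achievement of a target activated T-cell dose of" a stated figure, together with the absence of dose-limiting toxicity. A dosed patient without toxicity so far could be counted as a provisional success, and nothing excludes this. The error then reverses and an ineffective procedure is stopped too rarely. That reading also depends on when failures become known. If half are known at once, stopping at 0.5 is 0.076 / 0.064 / 0.055 for 2 / 3 / 4 pending; if all are, it returns to about 0.108.

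It is also fair to say that nothing was miscalculated. The boundaries and operating characteristics are right for the count they assume.

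**Conclusion.** The concern holds as an inconsistency between the rule and its table, not as an arithmetic error. The boundaries belong to patients with a known day +90 outcome, and the heading names a larger group. Followed literally, the table can contradict the criterion it is meant to implement.

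The size is two-sided and depends on an unstated choice. With 2 to 4 pending, early stopping at a true rate of 0.5 runs from about 0.02–0.04 (provisional successes) to about 0.22–0.36 (non-successes), against 0.108 printed. At 0.3 it runs from about 0.45–0.66 to about 0.90–0.95, against 0.833. It would be too strong to say that the 10% property is lost: counting only evaluated patients preserves it.

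These figures assume fixed accrual of 1 per month, the first 6 patients evaluated before patient 7, a look at every enrolment and, for the provisional reading, no failure known early. They illustrate the effect and are not bounds. The contradiction at 8 accrued, 6 evaluated and 1 success needs none of the accrual modelling. It should be fixed, because this rule decides whether accrual continues on the primary endpoint.

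**What to change.** 1. Re-head the first column *patients evaluated for the day +90 endpoint*.
2. State that pending patients are not counted, and whether a failure known before day +90 (missed cell dose or early dose-limiting toxicity) enters at once. The second choice matters: if half or all failures are assumed known at 0.5 month and enter then, evaluated-only stopping at a true rate of 0.5 is about 0.11 to 0.15.
3. Either state that the printed operating characteristics assume immediate outcomes, or rerun them with the lag at 1 patient per month. In both cases say whether "Achieved Sample Size" means enrolled or evaluated patients.

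The cost is one column heading, a few sentences and, if chosen, a short rerun. The criterion, the boundary values and the maximum of 40 do not change. The downside is slightly less favourable figures: with failures counted only at day +90, stopping at a true rate of 0.3 is about 0.79 to 0.82 instead of 0.833.

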Overall Response (CR+PR): We will assess overall response (CR+PR).

Infections: We will assess the rates of infection.

Criteria for Removal from Study:

1. **"Subjects" voluntary withdrawal from protocol.**
2. **Noncompliance of the patient with protocol requirements**
3. **After 5 years of treatment completion**
4. **Subject lost to follow-up**
5. **Decision by the investigators that withdrawing is in the subject's best interest**
6. **Pregnancy**
7. **Termination of the study by the investigator, IRB, or FDA**
8. **Unacceptable toxicity and other safety reasons- as defined by the stopping rules below.**
9. **Patients who experience DLT will not be eligible for retreatment.**

Toxicity Management, Stopping Rules and Study Termination

Only unexpected SAEs that are related to the activated autologous T cells would define a stopping rule.

Management of toxicity

Autoimmune toxicity associated with activated autologous T cells has been managed with a course of pharmacologic immunosuppression such as systemic corticosteroids.

Dose Limiting Toxicity

Dose limiting toxicity (DLT) is defined as any one or more of the following which occur after the T Cell Infusion:

1. Any Grade 3 or higher non-hematological adverse event other than fevers lasting less than 72 hours must will be considered DLT. Any prolonged grade 4 or higher hematologic toxicity (longer than 7 days) due to study treatment will be considered as DLT (CTC v4.03 CTCAE).
2. Allergic reaction or urticaria grade 3 or higher and deemed related to T cells (as determined using the Common Terminology Criteria for Adverse Events v4.03).
3. Grade 2 or greater autoimmune phenomena
4. Grade 4 or higher hematologic toxicity with the exception of any preexisting AE due to prior treatment or due to disease.

Stopping Rules

The statistical considerations section describes the primary stopping rule for the study, a rule which monitors patient success rate.

In addition, accrual to the study will be suspended to allow review with the institutional IRB if any death occurs among subjects who receive investigational agents due to the infusion of co-stimulated T-Cell product itself and not disease progression.

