If the study is prematurely halted based on preliminary information, it will be allowed to continue only if it is determined upon review that the incidence of adverse events is not exceedingly high for this patient population and that any death is not primarily due to the co-stimulated T-Cell therapy. If the study is not terminated early, it will continue until all patients have been treated with co-stimulated T Cells and completed all follow up evaluations.

Data Safety Monitoring Board / DSMB at MDACC:

Select the name of the data safety monitoring board (DSMB) monitoring this protocol:
Not Applicable

Please explain:

As of PDOL Version 07, this study is not randomized nor blinded.

Protocol Monitoring:

Does this protocol have a schedule for interim and final analysis? Yes

Provide a summary or schedule of interim analysis.

We will use a Bayesian sequential monitoring rule (Thall et al (ref)) to monitor the primary endpoint of the study. See the Statistical Considerations section for details.

Protocol Monitoring Plan:

Patient registration and monitoring will be performed by the MD Anderson IND Office according to institutional policies.

Intellectual Property:

1. Does this study include any agents, devices, or radioactive compound (or No drug) manufactured at MD Anderson Cancer Center or by a contract manufacturer?

Investigational New Drugs (IND):

Does this protocol require an IND? Yes

Who is the IND Holder/Regulatory Sponsor?

MD Anderson

IND Number: 16501

Please "Compose" an Investigator's Brochure Cover Letter. For technical assistance, contact the PDOL Help Desk, [contact].

Investigational Device (IDE):

Does this study utilize an Investigational Device? No

Moon Shots Program

Will your protocol be funded by the Moon Shots Program? Yes

Specific Disease Site(s): Chronic Lymphocytic Leukemia (CLL)

Platform(s): Applied Cellular Therapy (ACT)

Sponsorship and Support Information:

Does the Study have a Sponsor, Supporter or Granting Agency? Yes

Sponsor Name: Moon Shot Program

Support Type: Other: CLL

This Sponsor/Supporter/Granting Agency will receive data.

Regulatory Requirements

Radioactive Material:

Does this study involve the administration of radioisotopes or a radioisotope labeled agent?

No

[Click here for help](#)

Biosafety:

Does this study involve the use of Recombinant DNA Technology? No

Does this study involve the use of organisms that are infectious to humans? No

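### Must the plan change because it does not say what follows a DLT in the first six patients, and because the early-stopping table leaves that enrollment hold out?

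*Combined protocol and SAP*

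**What the plan says.** Under Safety Monitoring in the Statistical Considerations, two controls on enrollment stand close together.

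- **The Bayesian success rule.** Accrual ends if the posterior probability that the 90-day success rate exceeds 0.50 falls below 0.025, with a Beta(1,1) prior and at least 6 patients enrolled first. Of this rule the text says "This stopping rule was chosen to assure that the probability that the trial will stop early would be approximately 10" per cent at a true success rate of 50%. Its table is headed "Operating Characteristics for Success Monitoring Rule".
- **The staggered start.** "We will enroll 3 patients and then wait till all 3 have reached +90 days without DLT before enrolling more patients". Then: "At that time point 3 additional patients will be enrolled and we will wait till they have all reached" day +"90 days and without DLT before enrolling the remaining patients".

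Two other places bear on the question. The Stopping Rules section says "The statistical considerations section describes the primary stopping rule for the study, a rule which monitors patient success rate", and adds only product-related death. The same section then gives a general route back: "If the study is prematurely halted based on preliminary information, it will be allowed to continue only if it is determined upon review" that adverse events are not too frequent for this population and that no death was mainly due to the product.

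**The concern.** Read literally, the staggered start can lock. Once one of the first 3 patients has a DLT, the condition that all 3 reach day +90 free of DLT can never be met, and the same holds for patients 4 to 6. Nothing says whether enrollment has then ended or is paused. A study team with a DLT at patient 2 would look in vain for the answer, and safety is part of the primary objective.

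The second worry is numerical. The sentence giving the figure of about 10% speaks of the trial stopping early, and the staggered-start paragraph sits between that sentence and the table. A reader could take the table as describing the whole trial. If halts at 3 or 6 patients were final, the trial would end very early more often than the table shows, even where the product succeeds in most patients.

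**Working it through.** **Inputs from the plan (Statistical Considerations).** Beta(1,1) prior; cut-off 0.025; looks after every patient from n = 6 to 39; maximum 40; a DLT counts as a failure, and a failure can also come from missing the dose target alone.

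**Step 1: boundaries.** With s successes in n patients the posterior is Beta(1+s, 1+n−s), and accrual stops if Pr(rate > 0.5) < 0.025. At n = 6, s = 0 gives 0.5^7 = 0.0078 (stop) and s = 1 gives 0.0625 (continue), so the boundary is 0, as tabled. At n = 39, s = 13 gives 0.0192 (stop) and s = 14 gives 0.0403 (continue), so the boundary is 13, as tabled. Every boundary from 6 to 39 agrees.

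**Step 2: the plan's own early-stopping figures.** Exact binomial recursion, without the staggered start:

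| True success rate | Stated | Recomputed |
|---|---|---|
| 0.3 | 0.833 | 0.8332 |
| 0.4 | 0.413 | 0.4131 |
| 0.5 | 0.108 | 0.1077 |
| 0.6 | 0.018 | 0.0178 |
| 0.7 | 0.002 | 0.0021 |

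The sample-size percentiles also agree. The table is correct for the rule it names and contains no effect of the staggered start.

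**Step 3: what a permanent hold would do.** The documents give no DLT rate, so q below is an assumption, with patients taken as independent. The chance of a halt at patient 3 is 1 − (1−q)^3. The chance of a first halt at patient 6 is (1−q)^3 − (1−q)^6. For q = 0.05 these are 1 − 0.8574 = 0.1426 and 0.8574 − 0.7351 = 0.1223, together 0.2649.

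Total early stopping is 1 − (1−q)^6 plus the probability that the first six are free of DLT and the Bayesian rule stops later. In that second part, the success probability is p/(1−q) for the first six patients and p afterwards. At p = 0.50:

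- q = 0.01: 0.0585 + 0.0984 = 0.157
- q = 0.05: 0.2649 + 0.0678 = 0.333
- q = 0.10: 0.4686 + 0.0410 = 0.510

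Expected sample size falls from 37.4 to 35.6, 29.0 and 22.3. At p = 0.70 and q = 0.05 the total is 0.266, against the stated 0.002.

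**Step 4: what a reviewable hold would do.** Let a fraction L of halts be lifted (also an assumption). At p = 0.50:

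| L | q = 0.01 | q = 0.05 | q = 0.10 |
|---|---|---|---|
| 0 | 0.157 | 0.333 | 0.510 |
| 0.5 | 0.133 | 0.224 | 0.323 |
| 0.9 | 0.113 | 0.132 | 0.153 |
| 1 | 0.108 | 0.108 | 0.108 |

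The result therefore depends on L, a procedural matter, and on q, which is not given.

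**Step 5: which reading the text favours.** For the staggered start the plan speaks of waiting; for the Bayesian rule it speaks of stopping and terminating. It sets a minimum of 6 patients before stopping, which fits poorly with a final end at 3, although that sentence belongs to the Bayesian rule. The Stopping Rules section does not list the staggered start. The review clause that follows names no single trigger, and its test, whether adverse events are too frequent, suits a DLT. Together these lean towards a pause with review, that is, towards the last rows of the table in Step 4. This is inference: no sentence links the review to the staggered start.

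**The case for a change.** The best case for a change is that safety is part of the primary objective, no data safety monitoring board is named, and the study team assesses the rules itself. The consequence of an early DLT is then better written down beforehand than decided afterwards, and a sentence or two would do it. The point about wording stands: the text does not name the consequence, and one sentence links the 10% to the trial and not only to the rule.

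It does not stand as a fault in the operating characteristics. The 10% sentence begins with the stopping rule as its subject, the table is introduced as belonging to that rule, and the heading names it. Reporting one rule's properties under that rule's name is ordinary practice. The large figures in Step 3 need both a final halt, which the documents do not establish, and a DLT rate, which they do not give. The document is also a protocol abstract, and this review cannot see whether procedures for the first cohorts are set out elsewhere.

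Two neighbouring points should not be folded in. On product-related death, Safety Monitoring says that it "will be considered unacceptable and the study will be stopped", while the Stopping Rules section speaks of suspending accrual for review. The review clause largely bridges the two, and the passages must be reconciled as a matter of wording. The DLT definitions under Primary Endpoint and under Dose Limiting Toxicity differ in the grade at which non-hematologic events count. Those passages must be reconciled too, but that is a separate question from what follows a DLT.

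**Conclusion.** The observation is accurate, but it does not call for a change to the plan. The stated 10% and the table are right for the Bayesian success rule, to the three decimals given, and the heading confines them to it. The missing consequence of a DLT in the first six patients is a gap in procedural detail. The study team can fill it sensibly through the existing review clause, and the text leans that way.

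At a true success rate of 0.50 the effect on early stopping runs from none (0.108, all halts lifted) to 0.157, 0.333 or 0.510 (no halts lifted; assumed DLT rates of 1%, 5% and 10%). The upper figures would matter only if a halt were final, and recalculation would be warranted only then. This conclusion takes no position on how a DLT at that stage should be handled clinically.

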The collected blood will be expanded ex-vivo by aAPCs. The expansion will take 14 days. The process can generate 2.5×10^9 to 1×10^{10} cells which will be formulated for infusion in 100-500 mL of human serum albumin infusion buffer. Cells for later additional infusions may be cryopreserved.

Patients will receive a single infusion of ex-vivo expanded autologous T-Cells. Optimal dose will be 1×10^{10} activated T cells (+/- 20%), however for patients who cannot achieve that dose, a lower dose of activated T cells that meets release criteria may be infused at the discretion of the Principal Investigator.

Additionally, patients who have been previously treated on study, and subsequently need additional infusions may be retreated with previously cryopreserved expanded cells at the same or lower dose level. Retreatment will occur 6-12 months after the first infusion as long as no DLT was noted with the first infusion. These patients will be only followed for toxicity. Patients who have previously experienced DLT will be removed from the study and will not be eligible for retreatment.

Packaging and Administration

The T cells will be administered via intravenous infusion over 20-30 minutes without a leukocyte filter.

Autologous co-stimulated T-cell infusion

1. Co-stimulated T-cells will be infused at a dose of approximately 1×10^{10} (+/-20%). If optimal cell dose of 1×10^{10} (+/-20%).) is not achieved, a lower dose of activated T cells that meets release criteria may be infused at the discretion of the Principal Investigator.
2. Patients will receive premedication with Acetaminophen 650 mg PO and/or diphenhydramine 25-50 mg IV at least 30 minutes prior to infusion.
3. Additional orders: Acetaminophen 650 mg PO q4h for temperature > 38°, diphenhydramine 25 mg IVPB q3-4h prn and meperidine 25 mg IVPB q 2h prn for chills (if chills persist inform MD). Anaphylaxis precautions: Following drugs should be available at bedside: 3cc epinephrine 1:1000, diphenhydramine 25 mg IV and hydrocortisone 100 mg IV. In the event of a severe allergic reaction (e.g., anaphylaxis, bronchospasm, hypotension) or serious adverse reaction (i.e., cardiac failure, respiratory failure, severe nausea and vomiting) to the T Cell therapy, the infusion of the autologous T Cells will be stopped immediately and the patient will be provided with the supportive care deemed necessary by the physician and medical staff at the clinic.

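### The 3-then-3 run-in clears on DLT-free status whatever dose was infused, so DLT results pool doses and may rest on few patients at the planned dose

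*Combined protocol and SAP*

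**What the plan says.** Under Statistical Considerations, Safety Monitoring, enrolment is staggered: "We will enroll 3 patients and then wait till all 3 have reached +90 days without DLT before enrolling more patients". Then: "At that time point 3 additional patients will be enrolled and we will wait till they have all reached" day +"90 days and without DLT before enrolling the remaining patients". The only condition in either step is absence of DLT. There is no dose condition, no definition of a patient evaluable for the run-in, and no replacement provision. The Overview counts day +90 from infusion, so in practice the gate counts infused patients.

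The Proposed Treatment/Study Plan sets an optimal dose of 1×10^10 ± 20%, that is 8×10^9 to 1.2×10^10. On manufacturing it says: "The process can generate 2.5×10^9 to 1×10^{10} cells". The planned dose is thus the upper end of the stated yield. When it is not reached, "a lower dose of activated T cells that meets release criteria may be infused at the discretion of the Principal Investigator". This permission appears twice and carries no numeric floor.

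Dose enters monitoring only through the Primary Endpoint, where success is "achievement of a target activated T-cell dose of $1 \times 10^8 \pm 20\%$ and the lack of dose limiting toxicity". That target is a hundredth of the dose in the treatment plan. Secondary Analyses covers immune reconstitution, response and infection. No section separates DLT by dose received.

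**The concern.** Safety is half of the primary objective, and the run-in is the only quantitative check in the plan that looks at DLT alone. A patient given less than the planned dose counts toward clearing it exactly as a planned-dose patient does. Six DLT-free patients could then be read as evidence about 1×10^10 cells when only one or two of them received that dose. The final DLT figure has the same weakness, because nothing asks for it to be broken down by dose. If DLT risk rises with dose, the pooled figure would understate the risk at the planned dose.

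**Working it through.** **The plan's own figures.** The documents give no operating figure for the 3-then-3 gate. They do give them for the Bayesian success rule, the possible backstop. With a beta(1, 1) prior and the 0.025 cut-off, every tabulated boundary from 6 to 39 patients reproduces. Exact binomial recursion, looking after each patient from 6 to 39, gives early-stopping probabilities of 0.833, 0.413, 0.108, 0.018 and 0.002 at success rates 0.3 to 0.7. All match the table.

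**Inputs for the gate.** Six patients (3 + 3) and the planned window of 1×10^10 ± 20% come from the documents. The share q of patients infused in that window does not, so it is an assumption shown over a range. The lowest value, 27%, is what yields spread uniformly over the stated range would give: (10 − 8)/(10 − 2.5) = 0.267. The documents state no yield distribution.

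**How many run-in patients are at the planned dose.** The number is Binomial(6, q). P(none of the first 3) = (1 − q)^3 and P(none of 6) = (1 − q)^6.

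| Assumed q | None of first 3 | None of 6 | At most 2 of 6 |
|---|---|---|---|
| 90% | 0.1% | <0.1% | 0.1% |
| 75% | 1.6% | <0.1% | 4% |
| 50% | 12.5% | 1.6% | 34% |
| 27% | 39% | 16% | 80% |

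**What a clean gate then shows.** With 0 DLTs in m planned-dose patients, the one-sided 95% upper limit for the DLT rate at that dose is 1 − 0.05^(1/m):

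- m = 6: 39%
- m = 3: 63%
- m = 2: 78%
- m = 1: 95%
- m = 0: no information

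**Illustration with a dose gradient.** The documents give no relation between dose and DLT. Suppose the DLT risk is 30% at the planned dose and 5% below it. The gate clears with probability 0.70^m × 0.95^(6 − m):

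- six at the planned dose: 0.12
- two: 0.40
- one: 0.54
- none: 0.73

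**The success rule as backstop.** Suppose first that its target means the planned dose. The posterior probability that the success rate exceeds 0.50 is:

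- 0 successes in 6: 0.0078, stop
- 1 in 6: 0.0625, continue
- 1 in 7: 0.035, continue
- 1 in 8: 0.0195, stop

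If no DLTs occur, the success rate equals q. The rule then stops early with probability 0.92 at q = 27% (median stop at 14 patients) and 0.108 at q = 50%. If the target is read as printed, 1×10^8 ± 20%, the rule does not check the treatment-plan dose at all.

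**The case against.** The strongest reply is that the success rule already requires target dose and no DLT together. If the target is the planned dose, zero of six stops accrual, and a low q usually ends the trial early. This stands, and it rules out a stronger reading that a reader might infer: that the gate could clear with nobody at the planned dose and the other 34 patients then receive it in full. With no successes in six, accrual stops. At q = 27%, only about 9 of the 34 would be expected to reach the dose (0.267 × 34 = 9.1), and the trial would probably stop first.

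The backstop is still partial. It cannot act before six patients, so the first three can clear with none at the planned dose. It continues with one success in six or seven. It counts a missed dose and a DLT as the same failure, so it cannot isolate toxicity. It also depends on resolving 1×10^8 against 1×10^10. The stop or suspension for a product-related death does not cover non-fatal DLT.

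Three further replies have weight. The stated goal is the safety of the procedure, which includes discretionary lower doses, and if dosing practice is stable the first six patients sample the same mix as later ones. That defends a pooled figure as a description of the procedure, but not as a statement about the planned dose. Second, the yield passage says what the process can generate, not how often, and the release criteria may limit how low an infused dose can be; low doses are foreseen but cannot be called likely. Third, the claim that the gate loses most of its power to detect a problem would rest wholly on an assumed dose gradient.

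**Conclusion.** The concern holds in limited form. As written, the run-in is blind to dose while lower doses are expressly allowed, so DLT results at the gate and at the end mix doses and may include few planned-dose patients. The size depends on q, which the documents do not give. The issue is negligible at 90% and small at 75%. At 50% it is material: there is a one-in-three chance of at most two planned-dose patients among six, and the success rule seldom intervenes. At 27% dilution is the norm, but the success rule would usually stop the trial if its target is the planned dose. The upper limits of 39%, 63%, 78% and 95% depend only on how many DLT-free patients received the planned dose. A dose-toxicity gradient is an assumption, and nothing here shows that the planned dose is unsafe.

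**What to change.** 1. Tabulate DLT with exact confidence intervals by dose received (inside versus below the planned-dose window), at the gate and at the end of the trial. Limit any safety statement about the planned dose to patients who received it. This costs one table and one sentence. The success definition already requires the infused dose to be known, and no treatment or enrolment changes.

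2. Reconcile the Proposed Treatment/Study Plan, Primary Endpoint and Safety Monitoring sections on the target dose (1×10^10 against 1×10^8) and on which patients the run-in counts, including those given less than the planned dose. The choice of rule is the sponsor's. For information, a gate restricted to planned-dose patients would need on average 6/q infused patients to obtain six: 6.7, 8, 12 and 22.5 at q = 90%, 75%, 50% and 27%. Tying it to the primary-endpoint window as now printed would exclude every patient at the treatment-plan dose, so the target must be settled first.

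3. The table also needs a single DLT definition. Primary Endpoint starts non-hematologic DLT at grade 4, while the Dose Limiting Toxicity section starts it at grade 3 (short fevers excepted). These must be reconciled too.
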